7.6 Interim Analyses and Data Monitoring

7.6.1 Planned Analysis Schedule

The trial objectives will be evaluated once, after completion of all planned assessments and database lock, at the end of the trial.

7.6.2 Practical Measures to Minimise Bias

To maintain the blind throughout the study immunogenicity data related to HIL-214 will not be provided to the blinded Veramed statistical analysis team until after DBL. Any programming of associated datasets and TFLs prior to study unblinding will be done using dummy data.

7.7 Multi-centre Studies

This is a multi-country study with randomization stratified by country.

8 Summary of Study Data

All continuous variables will be summarised using the following descriptive statistics: n (non-missing sample size), mean, standard deviation, median, maximum and minimum. The frequency and percentages (based on the non-missing sample size) of observed levels will be reported for all categorical measures. In general, all data will be listed, sorted by site, trial vaccine and subject, and when appropriate by visit number within subject.

All summary tables, unless otherwise stated, will be structured with a column for each trial vaccine in the order (Placebo, HIL-214) and will be annotated with the total population size relevant to that table/trial vaccine, including any missing observations. The vaccine group labels can be found in

Table 6.

Table 6: Vaccine group labels for reporting

Output ordered by	Label for use in output	Description
Vaccine group	Placebo	2-dose series of placebo at 4 and 6 months of age, with concomitant routine pediatric vaccines at 2, 4 and 6 months of age
	HIL-214	2-dose series of HIL-214 at 4 and 6 months of age, with concomitant routine pediatric vaccines at 2, 4 and 6 months of age
	Total*	All subjects pooled

*Only presented for study population tables

All summary tables specified in this section will be produced using the randomized analysis set (unless otherwise stated) and will have a summary for each country, as outline in **Section 7.4** and overall.

8.1 Subject Disposition

Completion/withdrawal from the study and completion/discontinuation from trial vaccine regimen, together with reasons for withdrawal from the study or discontinuation from trial vaccine regimen will be listed and the following will also be tabulated:

- Number and percentage of subjects who completed the study
- Number and percentage of subjects who discontinued trial vaccine regimen early and the principal reason for discontinuation
- Number and percentage of subjects withdrawn from the trial vaccine regimen before randomization and the principal reason for withdrawal
- Number and percentage of subjects withdrawn from the study after randomization and the principal reason for withdrawal
- Number and percentage of subjects withdrawn from the study between Visit 2 and Visit 3 and the principal reason for withdrawal
- Number and percentage of subjects withdrawn from the study between Visit 3 and Visit 4 and the principal reason for withdrawal
- Number and percentage of subjects withdrawn from the study between Visit 4 and Visit 5 and the principal reason for withdrawal

For subjects who fail to meet the eligibility criteria the reasons for failure, including the inclusion/exclusion criteria that were not met will be summarized and listed. This output will use the enrolled analysis set.

The number and percentage of subjects that are randomized to each trial arm will be summarized by country and listed.

The number and percentage of subjects included in each analysis set and the reasons for exclusion will be summarized and listed.

The number and percentage of subjects who attended each scheduled visit (including the early withdrawal visit) will be summarized and listed.

8.2 Protocol Deviations

The number and percentage of subjects with at least one important protocol deviation will be summarized by deviation category (major/minor). Designation of important/not important and major/minor protocol deviations will be determined after review of the final list of protocol deviations during the blinded data review meeting. Protocol deviations which lead to exclusion from the per protocol analysis set will be considered both important and major. Other protocol deviations, such as those related to GCP, may also be considered important and/or major protocol deviations. The lead statistician will be responsible for the categorisation of protocol deviations and the categorisation will be approved by the sponsor.

All protocol deviations will be listed.

8.3 Demographic and Baseline Variables

Demographic and baseline variables will be summarised descriptively. The variables to be summarized in the demography table will all be evaluated at randomization and are as follows:

- Age (days)
- Age by category
 - <= 18 years old
- Sex
 - Male
 - Female
 - Other/Not Recorded
- Race
 - American Indian or Alaskan Native
 - Asian
 - Black or African American
 - Native Hawaiian or Other Pacific Islander
 - White
 - Mixed Race
 - Other
 - Not Reported
 - Unknown
- Ethnicity
 - Hispanic or Latino
 - Not Hispanic or Latino
- Country
 - Panama
 - USA
- Prior Vaccinations
 - Yes
 - No
- Breastfeeding status
 - Breastfeeding
 - Not breastfeeding
- Weight (kg)
- Length (cm)
- Head Circumference (cm)

8.4 Concurrent Illnesses and Medical Conditions

Medical history will be coded using the latest available version of the Medical Dictionary for Regulatory Activities (MedDRA®). The dictionary version used will be 25.1.

Concurrent illnesses and medical conditions will be classified as 'current' if the end date is on or after Visit 2, or the condition has been marked as ongoing. Illnesses and medical conditions that start and end before Visit 2 will be classified as past.

Past and current medical history will be listed for the randomized analysis set.

8.5 Prior and Concomitant Medications

Prior medication definition: If a subject takes a medication before Visit 2, this medication will be classified as 'prior medication'. With this definition, any medication recorded that has been taken for at least 1 day and has been stopped before Visit 2 will be considered as prior.

Concomitant medication definition: Prior medication not stopped before Visit 2 will be classified as 'concomitant medication'. Medication will be labelled as 'concomitant medication' when the start date is between Visit 2 and the final study visit (Visit 5) or, in case of early termination, on the date of the subject's last visit. With this definition, any medication that has been taken for at least 1 day between Visit 2 and Visit 5 will be considered as concomitant.

Medications will be coded according to the 2020 version of the World Health Organization Drug Dictionary (WHODD). Medical procedures will not be coded. Prior and concomitant medications will be listed for the randomized analysis set by trial vaccine group. Concomitant medications will be summarised.

Procedure history will be listed separately by the procedure reported term for the randomized analysis set by trial vaccine group. Concomitant medical procedures carried out during the study will be listed for the randomized analysis set.

9 Immunogenicity Analyses

All immunogenicity variables will be listed by subject within study center. Data will be summarised by trial vaccine group and country.

For all continuous immunogenicity variables a standard summary of the number of subjects with an assessment (n), geometric mean (with 95% CI), geometric standard deviation, median, Q1, Q3, minimum and maximum will be presented alongside the number of assessments below the LLOQ and LLOD and above the ULOQ. The number of subjects missing an assessment will also be summarized.

For categorical variables the count and percentage of subjects with antibody titers/concentrations over a pre-defined threshold, count and percentage of subjects achieving seroresponse to HIL-214, and 95% CIs for the percentages, computed using the exact Clopper-Pearson [1] method, will be presented.

9.1 Primary Immunogenicity Analysis

9.1.1 Estimands

The estimands used for the primary objectives, outlined in **Section 4.2.1**, and the methods for analysing the data are described further in this section.

9.1.1.1 Data Point Sets and Intercurrent Events

The DPS (which outline the analysis set used) and intercurrent event strategies used for each of the primary immunogenicity estimands and primary supplementary immunogenicity estimands are outlined in **Table 7**.

Table 7: Data Point Sets and Intercurrent Event Strategies for the Primary and Supplementary Immunogenicity Estimands

Estimand	DPS	Lack of compliance with the vaccine administration schedule (vaccine administration outside of required time window*)	Occurrence of death before Visit 4 (28 days post dose 2)	Use of concomitant medications or other vaccines
Primary immunogenicity estimands	DPS1	Principal Stratum Strategy: Such subjects are excluded from the analysis set	Principal stratum strategy: Data will not be imputed after death, meaning the subject will not be included in the analysis	Treatment Policy strategy: Data will be used as collected
Supplementary immunogenicity estimands for the primary endpoints	DSP2	Treatment Policy Strategy: Data will be used as collected	Principal stratum strategy: Data will not be imputed after death, meaning subjects will not be included in the analysis	Treatment Policy strategy: Data will be used as collected

*This window will be defined at the blinded data review meeting (BDRM)

9.1.1.2 Endpoints

All primary immunogenicity endpoints will be evaluated at Visit 4 and can be found in **Table 8**.

Table 8: Primary Immunogenicity Endpoints

Related Vaccine	Type of Endpoint	Endpoint
Infanrix Hexa/Vaxelis	Binary	Binary (yes/no) variable indicating anti-DT IgG concentration ≥ 0.1 IU/mL
		Binary (yes/no) variable indicating anti-TT IgG concentration ≥ 0.1 IU/mL
		Binary variable indicating anti-poliovirus neutralizing antibody titers $\geq 1:8$, for poliovirus types 1, 2 and 3
		Binary variable indicating anti-PRP IgG concentration ≥ 0.15 μ g/mL
		Binary variable indicating anti-HBsAg Ig concentration ≥ 10 mIU/mL
	Continuous	Anti-pertussis (FHA) concentrations
		Anti-pertactin (PRN) IgG concentrations
		Anti-toxoid (PTX) IgG concentrations
Prevnar 13	Continuous	Anti-pneumococcal IgG concentrations for serotypes 1, 3, 4, 5, 6A, 6B, 7F, 9V, 14, 19A, 19F, 18C, and 23F
Rotarix	Continuous	Anti-RV1 IgA concentrations

9.1.1.3 Analysis Methods

A primary immunogenicity estimand and a supplementary estimand will be created for all of the endpoints outlined in **Table 8**. Analyses will be completed for the subgroups defined in **Section 7.4**.

For the primary immunogenicity estimands a complete case analysis will be performed, meaning any subjects with missing data for the parameter of interest will be excluded from the analysis.

For the supplementary immunogenicity estimands for the primary endpoints the missing data will be accounted for by reweighting the estimates using the method of inverse probability weighting. See **Section 7.5.1** for more details.

For the binary primary immunogenicity endpoints a standard summary for the categorical outcome will be presented as well as descriptive statistics for the continuous values. Further, the difference in percentage of subjects in the vaccine group with the event and the percentage of subjects in the

placebo group with the event will be evaluated. This will be presented along with a 95% CI calculated using the Miettinen and Nurminen [2] method as shown in **Section 5.4.1**.

For all continuous primary immunogenicity endpoints the geometric mean titer/concentration (GMT/GMC) with 95% CIs and geometric standard deviation (GSD) will be calculated. The GMRs between the vaccine group and the placebo group along with a 95% CI will be calculated using the analysis of variance (ANOVA) model with natural logarithm of antibody titer/concentration as the response variable and trial arm as a factor. Where country is used as a covariate (see **Section 7.3**) the adjusted GMs will also be presented. Further details can be found in **Section 5.4.3**.

For all primary immunogenicity parameters a reverse cumulative distribution curve will be produced, with titer/concentration on the x-axis and the percentage of patients below the titer value on the y-axis. All graphs will contain the two vaccine groups which will be overlaid.

A forest plot, with 95% CI, will be made for each of the three routine vaccines. Forest plots presenting data for the difference in percentages will have a line at 0 to indicate no difference, and forest plots presenting the data using ratios will have a line at 1 to indicate no difference. Since the routine vaccines of Infanrix Hexa/Vaxelis have endpoints that evaluate the data as both a difference in percentage and a ratio, separate plots will be created. All of these plots will be presented by country, with the plots for the Prevnar 13 and Rotarix vaccines also presented overall.

9.2 Secondary Immunogenicity Analyses

9.2.1 Estimands

The estimands used for the primary objectives, outlined in **Section 4.2.2**, and the methods for analysing the data are described further in this section.

9.2.1.1 Data Point Sets and Intercurrent Events

Secondary Immunogenicity Estimands for the Secondary Endpoints:

Secondary immunogenicity estimands will use the same DPS and intercurrent event strategies as the primary immunogenicity estimands outlined in **Table 7**.

Supplementary Immunogenicity Estimands for the Secondary Endpoints:

Supplementary immunogenicity estimands for the secondary endpoints will use the same DPS and intercurrent event strategies as the supplementary immunogenicity estimands for the primary endpoints outlined in **Table 7**.

9.2.1.2 Endpoints

All secondary immunogenicity endpoints will be evaluated at Visit 4 and are all related to the HIL-214 vaccine.

The binary secondary immunogenicity endpoints are as follows:

- Binary variable indicating seroresponse to the HIL-214, where seroresponse is defined as at least a 4-fold increase from baseline in anti-norovirus GI.1 HBGA-blocking titers
- Binary variable indicating seroresponse to the HIL-214, where seroresponse is defined as at least a 4-fold increase from baseline in anti-norovirus GII.4 HBGA-blocking titers

The continuous secondary immunogenicity endpoints are as follows:

- Anti-norovirus GI.1 and GII.4 HBGA-blocking titers.
- Anti-norovirus GI.1 and GII.4 HBGA-blocking titers fold rise from baseline.

9.2.1.3 Analysis Methods

For the secondary immunogenicity endpoints data will only be analysed for the patients receiving HIL-214.

A secondary immunogenicity estimand and a supplementary estimand will be created for all of the endpoints outlined in **Section 9.2.1.2**. Analyses will be completed for the two country subgroups only, defined in **Section 7.4**.

For the secondary immunogenicity estimands a complete case analysis will be performed, meaning any subjects with missing data for the parameter of interest will be excluded from the analysis.

For the supplementary immunogenicity estimands for the secondary endpoints the missing data will be accounted for by reweighting the estimates using the method of inverse probability weighting. See **Section 7.5.1** for more details.

For all binary secondary immunogenicity endpoints a standard categorical summary will be presented. SRR is defined in **Section 5.3.2.2**.

For all continuous secondary immunogenicity endpoints a standard continuous summary of the outcome will be presented alongside the GM and GMFR and their confidence intervals. Where country is used as a covariate (see **Section 7.3**) the adjusted GMs will also be presented.

For all secondary immunogenicity parameters a reverse cumulative distribution curve will be produced, with titer/concentration on the x-axis and the percentage of patients below the titer/concentration value on the y-axis. All graphs will present the two vaccine groups which will be overlaid.

Line graphs and boxplots summarizing the GMT for each trial vaccine group for the serotypes GI.1 and GII.4 will also be produced. These outputs will both have the visits of baseline and Visit 4 on the x-axis and the GMT on the y-axis, presenting data on the log scale.

Bar plots for seroresponse, with 95% CIs, will also be created with the results for placebo and HIL-214 stacked next to each other and separate sets of bars for the serotypes GI.1 and GII.4.

10 Safety Analyses

All safety analysis is defined in this section. Along with the following summaries, all safety endpoints will be listed by vaccine group. Where summaries are presented overall, after first dose and after second dose subjects will be summarised under the trial vaccine they receive for that period. If a subject receives HIL-214 for either dose they will be summarised under HIL-214 in the overall summary.

All safety summaries of continuous variables will present n (non-missing sample size), mean, standard deviation, median, maximum and minimum. All safety endpoint and summaries will use the safety analysis set.

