5.2.2 Secondary Endpoints and Estimands

Secondary estimand (immunogenicity):

Population:

Same as for the primary immunogenicity estimand.

Treatment strategy to be evaluated:

2-dose series of HIL-214 at 4 and 6 months of age, with concomitant routine pediatric vaccines at 2, 4 and 6 months of age.

Secondary immunogenicity endpoints (at 28 days post-dose 2, administered at 6 months of age):

- Anti-norovirus GI.1 and GII.4 HBGA-blocking titers.
- Anti-norovirus GI.1 and GII.4 HBGA-blocking titers fold rise from baseline.
- Binary variable indicating seroresponse to the HIL-214, where seroresponse is defined as at least a 4-fold increase from baseline in anti-norovirus GI.1 and GII.4 HBGA-blocking titers.

Population level summaries:

The following will be estimated at 28 days post-dose 2 (administered at 6 months of age):

- GI.1- and GII.4-specific geometric mean titers (GMTs) of HBGA-blocking titers.
- GI.1- and GII.4-specific geometric mean fold rise (GMFR) in HBGA-blocking titers.
- Seroresponse rates (SRR; i.e., percentage of subjects demonstrating seroresponse) for GI.1 and GII.4 serotypes.

Intercurrent event strategies:

Lack of compliance with the trial vaccine administration schedule, occurrence of death before Visit 4 (28 days post-dose 2), and use of concomitant medications or other vaccines will be handled using the same strategies as for the primary immunogenicity estimand.

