13.1.2 Immunogenicity Analysis

Immunogenicity data will be summarized by trial arm, for each licensed vaccine and corresponding immunogenicity assay, at all relevant time points, using:

- GMTs or GMCs and GMFR (as applicable) with 95% confidence interval (CI), geometric standard deviation (GSD), and minimum and maximum values, and
- Count and percentage of subjects with antibody titers/concentrations over pre-defined threshold, count and percentage of subjects achieving seroresponse to HIL-214, and 95% CIs for the percentages, computed using exact Clopper-Pearson method [17].

Assessment of primary objective:

The primary immunogenicity objective will be assessed using 95% CIs for differences in proportion of subjects with antibody concentrations/titers above a pre-specified threshold, computed by the Miettinen and Nurminen method [18], and 95% CIs for the geometric mean ratios, computed using the analysis of variance (ANOVA) model with natural logarithm of antibody titer/concentration as the response variable and trial arm as factor. Analyses will be done by licensed vaccine; for those vaccines used in more than one country, analyses will be repeated by country.

To address non-compliance with the vaccine administration schedule, a hypothetical strategy will be used under the assumption that lack of compliance is not related to the immune response to the routine pediatric vaccines and therefore, that infants who were not compliant with the vaccination schedule do not differ from the infants who did comply with regard to their immune response measurements. Hence, the primary immunogenicity analysis will be based on infants who were compliant with the vaccine administration schedule (i.e. received all doses of routine

CONFIDENTIAL

vaccines and trial vaccine within the allowed windows). According to the treatment policy strategy, blood sample results obtained after use of concomitant medications or other vaccines will be included in the analysis. Handling of missing data resulting from missing blood draws, non-evaluable samples (not enough volume), and blood draws outside the window will be described in the SAP.

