4.2.2 Secondary Endpoints and Estimands

Secondary Immunogenicity Estimands:

Population:

Same as for the primary immunogenicity estimands.

Treatment strategy to be evaluated:

- 2-dose series of HIL-214 at 4 and 6 months of age, with concomitant routine pediatric vaccines at 2, 4 and 6 months of age.

Secondary immunogenicity endpoints (at 28 days post-dose 2, administered at 6 months of age):

- Anti-norovirus GI.1 and GII.4 HBGA-blocking titers.
- Anti-norovirus GI.1 and GII.4 HBGA-blocking titers fold rise from baseline.
- Binary variable indicating seroresponse to the HIL-214, where seroresponse is defined as at least a 4-fold increase from baseline in anti-norovirus GI.1 and GII.4 HBGA-blocking titers.

Population level summaries:

The following will be estimated at 28 days post-dose 2 (administered at 6 months of age):

- GI.1 and GII.4-specific geometric mean titers (GMTs) of HBGA-blocking titers.

- GI.1 and GII.4-specific geometric mean fold rise (GMFR) in HBGA-blocking titers.
- Seroresponse rates (SRR; i.e., percentage of subjects demonstrating seroresponse) for GI.1 and GII.4 serotypes.

The analysis methods for the secondary endpoints used in the immunogenicity estimands are outlined in **Section 9.2.1.3.**

Intercurrent event strategies:

Lack of compliance with the trial vaccine administration schedule, occurrence of death before Visit 4 (28 days post-dose 2), and use of concomitant medications or other vaccines will be handled using the same strategies as for the primary immunogenicity estimands.

Supplementary estimands will use the treatment policy strategy for lack of compliance with trial vaccine administration schedule.

Rationale:

The secondary immunogenicity estimands aim to evaluate the immune response for to HIL-214 in pediatric subjects that receive all doses of childhood vaccines and HIL-214 in the correct time window.

The supplementary immunogenicity estimands aim to evaluate the immune response for to HIL-214 in pediatric subjects receive at least one dose of HIL-214 or placebo.

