7.4 Subgroups

Table 5 shows the routine vaccines used in each country.

Table 5: Routine Vaccines Used in Each Country

Disease(s)	Routine Vaccine	
	Panama	USA (and Puerto Rico)
DTaP-Hib-IPV-HepB	Infanrix Hexa	Vaxelis
PCV13	Prevnar 13	Prevnar 13
RV1	Rotarix	Rotarix

Since the routine vaccines used in Panama and the USA to protect against rotavirus and the pneumococcus are the same, presenting an overall summary for the endpoints related to these vaccines is planned. Analysis of the immunogenicity endpoints for rotavirus and pneumococcal vaccines will be presented both overall and by country.

As the hexavalent vaccines used will be different in Panama and the USA there is no plan to provide an overall summary for immunogenicity endpoints related to antigens contained in these vaccines.

Therefore, analysis of all immunogenicity endpoints related to the hexavalent vaccines will be presented by country only.

The following subgroups will be presented:

- Country:
 - Panama
 - USA

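### The secondary HIL-214 antibody analyses are planned by country only, so no overall GMT, GMFR or seroresponse estimate is prespecified for an estimand defined on a single population

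*SAP*

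**What the plan says.** - **Estimand.** Protocol 5.2.2 and SAP 4.2.2 define the secondary estimand without reference to country. The population is "Same as for the primary immunogenicity estimands", and the single treatment strategy is "2-dose series of HIL-214 at 4 and 6 months of age, with concomitant routine pediatric vaccines at 2, 4 and 6 months of age". The summaries are stated per strain, for example "GI.1- and GII.4-specific geometric mean titers (GMTs) of HBGA-blocking titers", with the GMFR and seroresponse rate alongside.
- **Protocol analysis.** The opening of protocol 13.1.2 summarises immunogenicity data by trial arm and names seroresponse to HIL-214 among the summaries.
- **SAP analysis.** SAP 9.2.1.3 restricts the arm, "For the secondary immunogenicity endpoints data will only be analysed for the patients receiving HIL-214", and then the scope: "Analyses will be completed for the two country subgroups only".
- **Reason for splitting.** SAP 7.4 says "As the hexavalent vaccines used will be different in Panama and the USA there is no plan to provide an overall summary" for the antigens in those vaccines. For PCV13 and RV1, where the product is shared, "presenting an overall summary for the endpoints related to these vaccines is planned", with country results as well. HIL-214 is not mentioned there.
- **Country as covariate.** SAP 9.2.1.3 promises adjusted geometric means where country is a covariate, and points to SAP 7.3. That section adds country only to ANOVA models for which an overall analysis alone is shown.

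**The concern.** The secondary objective asks one question about one regimen in one population. As written, the tables would answer it twice, once per country, with no planned answer for the trial as a whole. A trial-level figure would then have to be assembled after the fact, with pooling and country adjustment not fixed in advance. The SAP gives no reason for treating HIL-214 differently from PCV13 and RV1, and SAP section 13 does not list the restriction among its changes to the protocol. At stake is the prespecification and precision of a descriptive secondary result.

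**Working it through.** **1. Is an overall norovirus result planned elsewhere in the SAP?**
- Section 8 asks for results by country and overall, but only for the tables of that section (disposition, demography and the like).
- Section 9 says immunogenicity data are summarised by vaccine group and country, and does not mention overall.
- Section 9.1.1.3 plans overall forest plots for Prevnar 13 and Rotarix only.
- Section 10.1.2 (safety) uses nearly the same sentence as 9.2.1.3 but adds an overall analysis. The omission in 9.2.1.3 is therefore more than house style.
- Section 9.2.1.3 also plans reverse cumulative curves, GMT line graphs, boxplots and seroresponse bar plots, without saying whether they are by country or pooled.

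No overall table estimate is prespecified; the plots are undetermined.

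**2. Does the adjusted-mean sentence supply one?** SAP 7.3 needs an overall analysis, and read literally needs it to be the only one shown. The secondary endpoints have country analyses only, so they fail the condition on either reading. The sentence has no effect and sits badly with the restriction to country subgroups.

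**3. Does the SAP's reason for splitting reach HIL-214?** It is stated for hexavalent antigens. The protocol (8.1.1) describes one HIL-214 presentation and composition, and SAP Table 2 gives one set of assay limits per strain. PCV13 and RV1 are given with Infanrix Hexa in Panama and Vaxelis in the USA, and are still pooled.

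**4. Size.** The plan has no power calculation to reproduce. Its one figure is consistent: 400 at 1:1 gives 200 per arm.

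Assumptions: at least 100 US subjects (protocol 4.2) at 1:1 gives 100/2 = 50 US infants in the HIL-214 arm, leaving 200 − 50 = 150 in Panama, with no loss. The 100 is a minimum, so 50 is the low end for the US. The documents give no seroresponse rate or SD, so ranges are shown.

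Seroresponse, exact Clopper-Pearson 95% CI: lower limit = Beta(0.025; x, n−x+1), upper limit = Beta(0.975; x+1, n−x); half-width = (upper − lower)/2.

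| Rate | US, n=50 | Panama, n=150 | Overall, n=200 |
|---|---|---|---|
| 50% | 35.5–64.5 (14.5) | 41.7–58.3 (8.3) | 42.9–57.1 (7.1) |
| 80% | 66.3–90.0 (11.8) | 72.7–86.1 (6.7) | 73.8–85.3 (5.8) |
| 90% | 78.2–96.7 (9.2) | 84.0–94.3 (5.1) | 85.0–93.8 (4.4) |

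Limits in %, half-widths in points.

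Sensitivity at 80%: an equal 100/100 split gives 8.3 points per country against 5.8 overall. With 80% evaluable (40/120/160) the half-widths are 13.3, 7.5 and 6.5.

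Geometric means, by the form in SAP 5.4.2: the CI limits lie a factor exp(1.96·SD/√n) from the estimate, with SD on the ln scale.

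| SD of ln value | US | Panama | Overall |
|---|---|---|---|
| 1.0 | 1.32 | 1.17 | 1.15 |
| 1.5 | 1.52 | 1.27 | 1.23 |

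For any common SD, the log-scale standard error relative to overall is √(200/50) = 2.0 in the US and √(200/150) = 1.15 in Panama.

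**The case against.** **The regimen differs by country.** The treatment strategy includes the concomitant vaccines, and the hexavalent brand differs. Interference between vaccines is what this trial studies, so the documents do not support saying that the hexavalent difference cannot bear on the norovirus response. This stands as a reason to keep country results. It does not explain their exclusive use: the SAP does not offer it for HIL-214 and pools PCV13 and RV1 despite the same difference.

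**A reader might infer that the estimand is never estimated for the whole trial.** That goes too far. The adjusted-mean sentence presupposes a pooled model, and the plots, some with confidence intervals, may be pooled. The section is inconsistent about pooling; what it lacks is a prespecified overall table estimate.

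**A reader might infer that the SAP breaks the protocol's rule that** "for those vaccines used in more than one country, analyses will be repeated by country". That sentence comes under the assessment of the primary objective and concerns licensed vaccines, so it does not govern HIL-214. The support from the protocol is the by-arm summary that opens 13.1.2 and the unsplit estimand in 5.2.2.

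**Nothing is lost.** Country counts give the crude pooled rate and its exact CI, and country n, geometric mean and GSD give the pooled GMT. This is true, but such pooling would not be prespecified. Nor does the wider interval breach any criterion, since the trial is descriptive with no precision target.

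**Conclusion.** The point holds as a gap in the plan for a descriptive secondary objective. SAP 9.2.1.3 prespecifies no overall table estimate of the HIL-214 GMT, GMFR or seroresponse rate, although the estimand is not split by country and the SAP's reason for splitting is given only for other antigens. The section also contradicts itself on pooling. It is an unexplained choice, not proof that splitting is wrong.

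Under the assumed 50/150 split, the overall interval for seroresponse is about half as wide as the US one and modestly narrower than the Panama one; a more even split narrows the contrast with the US. These figures depend on the assumed split, rates and SDs. No hypothesis test, power statement, primary endpoint or safety result is affected. The change is worth making because it costs almost nothing and gives the objective a planned trial-level answer.

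**What to change.** - **SAP 9.2.1.3:** present GMT, GMFR and seroresponse rate for GI.1 and GII.4 overall and by country, under both the secondary and the supplementary estimand. State for each plot whether it is overall, by country or both.
- **SAP 7.4:** add the norovirus endpoints to those shown overall and by country.
- **SAP 7.3:** either amend it so that country adjustment applies to the overall norovirus geometric means, saying how the countries are weighted, or delete the adjusted-mean sentence from 9.2.1.3. Changing 9.2.1.3 and 7.4 alone would leave that sentence without effect, because the literal condition in 7.3 would still not be met.
- If country-only results are intended, give the reason and list the restriction in SAP section 13.

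Cost: SAP wording and one extra column in existing tables. No new data, samples or assays are needed.
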